## PRÉCIS

Title: Translating a ‘Stand Up and Move More’ Intervention by State Aging Units to Older Adults in Underserved Communities

Objectives: To examine the effectiveness of a *Stand Up and Move More* intervention to reduce sedentary behavior, increase physical activity, and improve functional performance and quality of life in older adults. A second objective is to examine the feasibility of implementing the *Stand Up and Move More* intervention by State Aging Units to underserved communities in the state.

Design and Outcomes: A randomized controlled trial will be conducted with older adults from four counties in Wisconsin (i.e., Dane, Rock, Iowa, and Vilas counties) randomized to intervention or wait-list control groups. Sedentary behavior, physical activity levels, functional performance, and health-related quality of life will be assessed at baseline (before the intervention begins), at week 4 (after the intervention), and week 12 (follow-up) to examine the effectiveness of the program. Feasibility of implementing the program by our community partners will be assessed via semi-structured interviews.

Intervention and Duration: The intervention consists of an introductory session, four weekly sessions (i.e., once/week for four weeks), and a refresher session at 8 weeks, and will be delivered by community partners in each county. Based on self-regulation theory, the sessions will elicit ideas from older adults regarding how they can reduce their sitting time, help them set practical goals, develop action plans to reach their goals, and refine their plans across sessions to promote behavior change.

Sample Size and Population: Eighty sedentary adults greater than 55 years of age from four counties made up predominantly of rural older adults and older African American adults will be randomly assigned to intervention (n = 40) or wait-list control (n = 40) groups.

## **PARTICIPATING COMMUNITY PARTNERS AND SITES**

University of Wisconsin-Madison: This study involves collaboration between the UW-Madison and 4 county sites. The UW-Madison is the lead site and will serve as the IRB of record for this study.

## **BACKGROUND AND SPECIFIC AIMS**

The number of adults  $\geq 65$  years in the U.S. is expected to more than double from 40 million in 2010 to 87 million by 2050. With the aging of the population, a growing number of older adults face complex health issues that often lead to functional limitations. Preservation of functional performance in community-dwelling older adults is critical to maintaining independence and quality of life, as well as containing costs in the older adult population. Since the elderly represent the fastest growing segment of our population, maintaining independence throughout later life has emerged as an important public health goal. Interventions that remediate functional decline are of high priority. Exercise has been effective in combating functional decline but older adults tend to have low levels of exercise, and few report meeting current national guidelines (i.e., 150 minutes of moderate intensity physical activity/week) which may be

challenging, especially for older adults with existing limitations. There is a clear need for interventions that bridge the gap between inactivity and current exercise guidelines providing older adults with an attainable transition to a more active lifestyle.

A growing body of research demonstrates the negative health consequences of sedentary behavior (i.e., too much sitting). Older adults are one of the most sedentary age groups spending 60-70% of their waking hours in sedentary activities. This amount of sedentary time increases the risk of functional decline, chronic diseases, and premature mortality. Emerging research suggests breaks in sedentary time (i.e., standing up) are associated with better health and function in older adults. Thus, interventions that **shift the focus** from increasing exercise to breaking up extended sitting time by standing up and moving more throughout the day may be **feasible for older adults to do** but there is limited research examining the benefit of such interventions. With funding from the Greater Wisconsin Agency on Aging Resources, we recently developed a behavior change intervention based on self-regulation theory and designed to help older adults break up extended sitting by standing up multiple times throughout the day. Preliminary examination of the intervention, in collaboration with our community partner the Rock County Council on Aging, indicated the intervention was feasible for staff to implement, participants expressed high satisfaction with the program, sedentary time decreased by approximately 1 hour/day ( $p < 0.05$ ), there were moderate effect size increases in physical activity, and large effect size improvements in mobility and vitality in a small sample of older adults. In addition, reductions in sedentary time were still evident four weeks after the intervention ended. These results provide preliminary evidence that our community-based behavior change intervention effectively reduced sedentary behavior, and importantly, could be sustained after the intervention ended. The purpose of the proposed research is to expand upon these initial promising results and examine the effectiveness as well as the feasibility of translating a *Stand Up & Move More* intervention by State Aging Units to underserved communities in the state.

**Aim 1:** To examine the effectiveness of a *Stand Up & Move More* intervention to reduce sedentary behavior, increase physical activity, and improve functional performance and quality of life in older adults. *Working Hypothesis:* It is hypothesized that there will be significant reductions in the primary outcome of sedentary behavior and increases/improvements in the secondary outcomes of physical activity, functional performance and health-related quality of life in the intervention group compared to no significant changes in the wait-list control group.

**Aim 2:** To examine the feasibility of implementing a *Stand Up & Move More* intervention by State Aging Units to underserved communities in the state. *Working Hypothesis:* It is hypothesized that the intervention to reduce sedentary behavior will be feasible to implement by State Aging Units to older adults in underserved communities.

The intervention we are proposing to test statewide was developed with community collaborators. Sitting less seems simple but intervention is required to get older adults to do it. If breaking up sitting time by standing up and moving more throughout the day proves to be effective then we will have identified a **practical** intervention with the potential to improve the health and function of older adults that could be translated to communities across the country.

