**Participants:** A power analysis was performed to estimate optimal sample size for detecting potential differences between intervention and wait-list control groups in sedentary behavior using a repeated measures design, with an alpha of 0.05, a power of 0.80, and a medium effect (0.57). Results from the G-power analysis indicated a total of 68 participants (34 per group) would be needed for the proposed study but we have increased sample size in anticipation of a potential attrition rate of approximately 20% (a minimum of 80 adults older than 55 yrs will be recruited). Four counties (Rock, Iowa, Vilas & Dane) will each recruit between 20–30 older adults who will be randomized to either the intervention group ( $n = 10–15$ ) or the control group ( $n = 10–15$ ). Inclusion criteria includes > 55 yrs, currently inactive or low active (i.e., < 60 min of physical activity/week), residents of Rock, Iowa, Vilas or Dane Counties, and residing in a home or an apartment. Exclusion criteria are low levels of sedentary behavior (i.e.,  $\leq 6$  hours/day); recent hospitalization (past month); uncontrolled medical conditions including uncontrolled hypertension (BP > 170 systolic or 100 diastolic), heart disease (symptoms of angina with minimal exertion in the past month), actively receiving chemotherapy or palliative care for cancer, stage 4 liver disease (e.g., cirrhosis with ascites or encephalopathy or history of

bleeding esophageal varices), end-stage renal disease (on dialysis or creatine > 4), or end-stage pulmonary disease (dyspnea at rest or with minimal exertion); severe arthritis or any orthopedic condition that could be made worse by standing up and moving more; inability to stand up without assistance of another person; and inability to speak or hear spoken English. Participants will be given a gift card up to \$50 upon study completion (\$20 for participating in the study plus \$10 per each of three assessments).

Recruitment of Participants: Staff from Aging Units in the four counties will recruit older adults from their counties for this study. Recruitment strategies include announcements in senior newsletters, at congregate dining sites, churches, and medical clinics. In addition, announcements will be posted on Aging Unit websites, and flyers will be sent to mailing lists of older adults in the various counties. These strategies were used in our pilot research and worked well in recruiting the estimated sample size.

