*Demographic and Health History Questionnaire*: At baseline, participants will be asked to complete a questionnaire regarding health status and demographic information (date of birth, sex, race, ethnicity, education, and marital status), current physical activity, smoking status, and current alcohol intake.

*Mediators of Behavior Change*: As suggested by NIH reviewers, we have added selected mediators of behavior change. Participants will complete questionnaires assessing self-regulation strategies, self-efficacy, and outcome expectancies.

*Adherence to the Intervention and Outcome Assessments*: Adherence to the *Stand Up and Move More* intervention workshop will consist of participants attending at least 50% of the sessions. As for outcome assessments, adherence to wearing the accelerometers will be defined as wearing the monitors 4 out of 7 days.

*Analyses*: The primary sedentary behavior outcome variables include total sedentary time, time spent sitting in long bouts (i.e.,  $\geq 60$  minutes), and sit-to-stand transitions as measured by the activPAL. These outcomes will be examined adjusting for monitor wear time if wear time differs between groups. We will also be able to analyze changes in specific domains of sedentary behavior (e.g., watching TV, reading) from data obtained from the sedentary behavior questionnaire. A 2 (groups) x 3 trials (pre, post-1, and post-2) repeated measures ANOVA will be used to examine differences between groups in changes in sedentary behavior before and following the intervention and control conditions. Similarly, for the secondary variables of physical activity, functional performance, health-related quality of life, and mediators of behavior change, a series of 2 x 3 repeated measures ANOVA's will be performed. Significant main effects and interactions will be assessed with planned contrasts. Effect sizes will be calculated to examine the magnitude of differences between groups as well as the magnitude of change from pre to post-intervention according to methods described by Cohen. In addition,

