correlational analyses will be performed to examine the relationship between sedentary behavior and the secondary outcomes. Significance will be set at  $p < 0.05$ . {Note: since sample size was estimated for our primary outcome variable of sedentary behavior, we recognize the potential limitation of our sample for secondary outcomes. However, if one or more of the secondary outcomes shows a trend in the direction of significance and/or shows a moderate to large effect size, the number of participants can be expanded in subsequent research to address a specific hypothesis}.

*Note:* Multiple imputation will be used to account for missing data (and attrition) under a missing-at-random assumption using MICE package in R. Longitudinal models for the outcomes at the two post-intervention visits will adjust the pre-intervention value as a covariate and explicitly model changes in the outcomes over time. Intervention workshop will be included in the included model as a random effect to account for correlations in outcomes between subjects in the same workshop.

Feasibility: The feasibility of implementing the program by our community partners will be assessed after the refresher session (at 8 wks) via semi-structured interviews. The Aging Unit Directors and Health Program Facilitators will be interviewed and asked about their satisfaction with the intervention, the ease and difficulty of implementing the program, and their likelihood of sustaining the intervention outside of a research study {*Note: Aging Units offer evidence-based health promotion programs to older adults in their counties which are funded by the Older Americans Act (OAA). When a new health promotion program is shown to be evidence-based (i.e., effective, translatable), Aging Units can use OAA funding to support and sustain implementation of the program*}. Interviews will be transcribed and coded, classified, and organized into main themes using thematic analyses. Feasibility of completing the program by older adults will be assessed after the refresher session (at 8 wks) on the basis of program adherence (i.e., attendance) and participant satisfaction (brief questionnaire).

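### Aim 1's hypothesis compares significance within each arm, which is not a test of the treatment effect and does not match the planned between-group analysis; no deciding test is named

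*Combined protocol and SAP*

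**What the plan says.** The Aim 1 working hypothesis (Background and Specific Aims) opens "It is hypothesized that there will be significant reductions in the primary outcome of sedentary behavior", extends the prediction to physical activity, functional performance and quality of life, and closes "in the intervention group compared to no significant changes in the wait-list control group". It is the only hypothesis stated for Aim 1, so it covers the primary outcome and every secondary outcome.

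The Analyses paragraph (Research Design and Methods) is framed differently. There a 2 x 3 "repeated measures ANOVA will be used to examine differences between groups in changes in sedentary behavior". It continues: "Significant main effects and interactions will be assessed with planned contrasts". The contrasts are not listed. Effect sizes are planned for "the magnitude of differences between groups as well as the magnitude of change from pre to post-intervention". A note at the end of that section adds a second model: "Longitudinal models for the outcomes at the two post-intervention visits will adjust the pre-intervention value as a covariate", with workshop as a random effect. The Participants paragraph bases the sample size on a difference between the two groups.

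**The concern.** Significance in one arm and non-significance in the other does not show that the arms differ. The pattern can arise by chance when both arms change by the same amount. It can also fail when the intervention works but controls improve enough to reach significance themselves.

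The Analyses section does not fully close this off. It never names the group-by-time effect, or any one contrast, as decisive for Aim 1. A time main effect is change common to both arms, yet a significant one is enough to start the unlisted contrasts. An analyst could follow the text, find the intervention arm significant and the control arm not, and report the hypothesis as supported. At stake is how the primary conclusion and all the secondary conclusions are read, and whether the randomised control arm is what supports them.

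**Working it through.** **Inputs from the Participants paragraph.** Alpha 0.05, power 0.80, effect 0.57, 68 evaluable participants (34 per group).

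**Assumptions.** Two-sided tests (sidedness is not stated), independent arms, equal SD of change, and a shared change of 0 to 0.8 SD of change. The documents give no expected control-arm change.

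**Step 1: the plan's own figure.** The 68 is reproduced by the between-groups test of a repeated measures ANOVA with 3 measurements, taking 0.57 as Cohen's d (so f = 0.57/2 = 0.285) and a correlation of 0.5 between measurements; the metric and the correlation are assumed.

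- Noncentrality = f² × N × m / (1 + (m − 1) × rho) = 0.285² × 68 × 3 / (1 + 2 × 0.5) = 8.285.
- Power is 0.810 at N = 68 and 0.798 at N = 66, so 68 is the smallest even total that reaches 0.80.

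The power basis is therefore between groups, not within arm. On these assumptions it is the group main effect, averaged over all three visits including baseline, and not the group-by-time effect.

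**Step 2: how often the worded pattern occurs with no treatment effect.** Each arm has a paired t-test with 33 degrees of freedom and critical value 2.035. For a shared change of s SD, the noncentrality is s × √34. Let u be the probability of a significant reduction and l the probability of a significant increase. Then

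P(pattern) = u × (1 − u − l).

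| Shared change (SD) | u | 1 − u − l | P(pattern) |
|---|---|---|---|
| 0 | 0.025 | 0.950 | 2.4% |
| 0.1 | 0.082 | 0.913 | 7.5% |
| 0.2 | 0.204 | 0.795 | 16% |
| 0.3 | 0.397 | 0.603 | 24% |
| 0.35 | 0.509 | 0.492 | 25% |
| 0.5 | 0.808 | 0.192 | 16% |
| 0.8 | 0.995 | 0.005 | 0.5% |

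Once l is negligible this is u(1 − u), which cannot exceed 0.25 and reaches it at u = 0.5. So 25% is a ceiling.

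**Step 3: the between-arm test on the same data.** In 200,000 simulated trials with a shared change of 0.336 SD, the pattern occurred in 25.1%. A two-sided between-arm t-test of change rejected in 4.9%.

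**Step 4: when the intervention works.** P(pattern) is now u in the intervention arm times (1 − u − l) in the control arm. The first effect is the plan's 0.57, read here as SDs of change; 0.8 is shown for comparison.

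| Extra change (SD) | Between-arm power | Pattern at control change 0 | 0.1 | 0.2 | 0.3 | 0.35 | 0.5 |
|---|---|---|---|---|---|---|---|
| 0.57 | 64% | 85% | 88% | 79% | 60% | 49% | 19% |
| 0.8 | 90% | 95% | 91% | 79% | 60% | 49% | 19% |

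The pattern falls below the between-arm test only when controls change appreciably: from about 0.3 SD for an effect of 0.57, and from about 0.2 SD for 0.8.

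**Step 5: the time main effect.** Approximated as a paired t-test on all 68 participants, a shared change of 0.35 SD is significant about 81% of the time with no treatment effect. The first step towards unlisted contrasts can therefore be met easily by change common to both arms.

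**The case against.** The strongest reply is that the sentence is a prediction and not a decision rule. The ANOVA is described as comparing change between groups, the second model adjusts for baseline, and the power calculation is between groups. Within-arm paired tests are not specified anywhere. Pre-to-post change appears only as an effect size, and contrasts after main effects and interactions are ordinary ANOVA wording. All of that stands. A reader might infer that Aim 1 will be declared met whenever the within-arm pattern appears, or that the trial carries a 25% false-positive risk. The documents support neither inference: no section makes the pattern a success criterion, and 25% needs a particular shared change.

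A reader might also infer that drift in both arms is likely, through regression to the mean from "Exclusion criteria are low levels of sedentary behavior" or through wearing monitors. The support is weak. Eligibility is asked by telephone before baseline, whereas the primary variables come from the activPAL at baseline and later, so much of any regression would already have happened. The sitting cut-off of 6 hours/day is far below the pilot average of almost 11. Monitors are worn at baseline too, so reactivity need not produce change. Shared change is possible, but its size is unknown. Nor does the pattern always lose power, as Step 4 shows.

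What the reply does not remove is the mismatch. The only stated hypothesis is within-arm, the deciding test is unnamed, and the contrasts are open.

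**Conclusion.** The point holds as a defect in wording and in specification. Aim 1's hypothesis is not a test of the treatment effect and disagrees with the plan's own between-group analysis and power basis, and nothing in the text rules out judging it within arms. If it were judged that way, the false-positive rate would depend on the change shared by both arms, from 0.5% to 25% over the assumed range, against about 5% for a between-arm test. This rests on 34 per arm, two-sided 0.05 paired tests, and independent arms with equal SD of change. It says nothing against the error rate of the planned ANOVA. The correction is worth making because it settles what the trial may conclude.

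**What to change.** In Aim 1, state the hypothesis as: the change from baseline in sedentary behavior, and in each secondary outcome, is more favourable in the intervention arm than in the wait-list arm. Delete the clause about no significant change in controls.

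In Analyses, state that:

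- Aim 1 is judged by the baseline-adjusted between-arm difference, with its 95% confidence interval, from the longitudinal model already described in the note on missing data;
- a time or group main effect alone is not evidence of an intervention effect;
- within-arm changes and pre-to-post effect sizes are reported descriptively, without p-values.

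The cost is a few sentences in two places. No new data, visits or participants are needed.

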## RESEARCH DESIGN AND METHODS

Previous Research: With funding from the Greater Wisconsin Agency on Aging Resources, research was conducted to develop an intervention to reduce sedentary behavior and examine the feasibility of implementing the intervention by a State Aging Unit in a community setting. The research was conducted in two communities in Rock County, Wisconsin which is made up of

small urban and rural communities. The older adults in these communities had high levels of sedentary behavior (averaging almost 11 hours of their waking hours per day sitting) and their function scores were below the population average. A 4-week intervention based on self-regulation theory and designed to break up extended sitting time by standing up multiple times during the day significantly ( $p < 0.05$ ) reduced sedentary behavior (60 min/day), was associated with moderate increases in light intensity physical activity (effect size = 0.52; 35 minutes/day), and large effect size improvements in mobility (i.e., gait speed; effect size = 0.74) as well as vitality (effect size = 1.15). Importantly, reductions in sedentary behavior were sustained 4 weeks after the intervention ended. Strategies used most often included standing up during television commercials, and spreading household chores out across the day. Additional strategies included getting up to get a drink of water, and setting a timer to stand up. Twenty participants (out of a total of 25) completed the 4-week program and 90% of the participants expressed high satisfaction with the program (e.g., “What a great program. It made me realize how much I sit during the day and helped me manage my sitting time”). Also, participants indicated that breaking up sitting time was more appealing to them than increasing exercise. Further, the intervention was found to be feasible for staff to implement. The director of the Rock County Council on Aging who led the workshops stated “The intervention worked because it was simple. It is not complex and that is the beauty of it.” Thus, our pilot results are quite promising and represent the development, preliminary feasibility, and piloting stages of the *Stand Up & Move More* intervention in a small sample of older adults.

**Design:** As a next step, a randomized controlled trial will be conducted with a larger sample of older adults from underserved communities. Older adults from 4 counties in Wisconsin (i.e., Dane, Iowa, Rock & Vilas) will be randomized into intervention or wait-list control groups (Note: a block randomization scheme will be used blocking for age). Our pilot data suggests an intervention design of one session per week for 4 weeks with a refresher session at 8 weeks is feasible and likely to sustain behavior change. The primary outcome measure is sedentary behavior while the secondary outcome measures include physical activity, functional performance, and health-related quality of life. Assessments will be completed at baseline, after the intervention (4 weeks) and at follow-up (at 12 weeks as suggested by our community partners as being a reasonable time for the older adults in the control group to wait for the next workshop to begin). Feasibility of implementing the intervention will be assessed via semi-structured interviews of the health program facilitators, while feasibility of completing the *Stand Up & Move More* program by older adults will be assessed by program adherence and participant satisfaction.

**Participants:** A power analysis was performed to estimate optimal sample size for detecting potential differences between intervention and wait-list control groups in sedentary behavior using a repeated measures design, with an alpha of 0.05, a power of 0.80, and a medium effect (0.57). Results from the G-power analysis indicated a total of 68 participants (34 per group) would be needed for the proposed study but we have increased sample size in anticipation of a potential attrition rate of approximately 20% (a minimum of 80 adults older than 55 yrs will be recruited). Four counties (Rock, Iowa, Vilas & Dane) will each recruit between 20–30 older adults who will be randomized to either the intervention group ( $n = 10–15$ ) or the control group ( $n = 10–15$ ). Inclusion criteria includes > 55 yrs, currently inactive or low active (i.e., < 60 min of physical activity/week), residents of Rock, Iowa, Vilas or Dane Counties, and residing in a home or an apartment. Exclusion criteria are low levels of sedentary behavior (i.e.,  $\leq 6$  hours/day); recent hospitalization (past month); uncontrolled medical conditions including uncontrolled hypertension (BP > 170 systolic or 100 diastolic), heart disease (symptoms of angina with minimal exertion in the past month), actively receiving chemotherapy or palliative care for cancer, stage 4 liver disease (e.g., cirrhosis with ascites or encephalopathy or history of

bleeding esophageal varices), end-stage renal disease (on dialysis or creatine > 4), or end-stage pulmonary disease (dyspnea at rest or with minimal exertion); severe arthritis or any orthopedic condition that could be made worse by standing up and moving more; inability to stand up without assistance of another person; and inability to speak or hear spoken English. Participants will be given a gift card up to \$50 upon study completion (\$20 for participating in the study plus \$10 per each of three assessments).

Recruitment of Participants: Staff from Aging Units in the four counties will recruit older adults from their counties for this study. Recruitment strategies include announcements in senior newsletters, at congregate dining sites, churches, and medical clinics. In addition, announcements will be posted on Aging Unit websites, and flyers will be sent to mailing lists of older adults in the various counties. These strategies were used in our pilot research and worked well in recruiting the estimated sample size.

Individuals who are interested in learning more/participating in the study will be instructed to call a designated phone number and leave a message. A trained research assistant will promptly (within 48 hrs) call the prospective participant back and give a general explanation of the study, ask if the individual is still interested in participating in the study, and inquire whether they are willing to complete a brief interview (i.e., phone screen) to determine eligibility. If the individual agrees to the interview, they will be asked questions based on the inclusion/exclusion criteria. Those individuals who are deemed eligible to participate in the study will be informed of the introductory meeting (i.e., date/time and location). Individuals who are not eligible to participate in this study will be thanked for taking time to answer questions but be told that they will not be able to participate due to the strict requirements for this research.

Introductory Meeting: An introductory meeting will be held in each county for older adults interested in participating in the study. Our community partners will arrange the meeting at a location convenient for participants in their county. The PI will attend the meeting and describe the study (i.e., inform prospective participants of the procedures, risks and benefits, and they are free to discontinue participation in the study at any point). Prospective participants will be provided with ample time to read the Informed Consent Form and have the opportunity to ask and obtain an adequate reply to any questions they may have. Individuals interested in participating in the study will then sign an informed consent document and baseline assessments will be completed.

Intervention to Reduce Sedentary Behavior: The intervention is based on self-regulation theory as self-regulation has been shown to be an important influence of physical activity behavior change. Self-regulation has been defined as a goal-guidance process aimed at the attainment and maintenance of personal goals. Successful strategies for behavior change reflect a recognition that people move toward the goals they set by a process of self-regulatory actions. Most of the self-regulation models include components essential to the process of self-regulation such as 1) **goals** about what people are trying to accomplish, 2) **self-monitoring** of personal behavior and how it links up to goals, 3) **feedback and information** about progress toward each goal, 4) **self-evaluation** of progress, and 5) **corrective behavior** leading to more effective movement toward goals. Strategies incorporated into the *Stand Up & Move More* intervention sessions include individual goal setting, development of action plans to meet goals, information dissemination, self-monitoring, group discussions & feedback, and various problem solving activities. During the intervention, participants are taught how to appropriately set and adjust goals, as well as self-monitor their activity (use of a small click counter every time they stand up and completing daily logs at home at the end of each day). In addition, based on feedback from NIH reviewers, social cognitive theory will also be incorporated as a foundation for the intervention because research indicates that both self-regulation strategies and self-efficacy are associated

with physical activity behaviors. Social Cognitive Theory proposes a theoretical link between self-regulation and self-efficacy, and Annesi et al. reported that use of self-regulation strategies was related to increases in self-efficacy for eating healthy and being more physically active in middle-aged adults. We will examine whether the same is true for older adults with regards to sedentary behavior in the current study.

Older adults will be asked to break up prolonged sitting (1 hour or more) with short breaks, e.g., get up and move for a couple of minutes multiple times throughout the day. Following the format of our successful pilot, participants will be asked, initially, to break up sitting time an extra 3-5 times/day progressing to 10-12 times/day by week 4. During the sessions participants will strategize on ways they can break up their sitting time safely in their home environment. In subsequent sessions, participants will share strategies that worked for them as well as be introduced to a list of other strategies used by Gardiner et al. (e.g., standing up and getting a drink of water). This will provide participants with a wide range of strategies and participants will choose which strategies to adopt across the 4 weeks. Each session builds upon the previous one with new information provided during each session. An overview of the sessions follows (with a summary table located in the supplemental material):

**Session 1:** Introduction and overview; group discussion on time spent sitting during the day and then participants will be asked to reflect on their current sitting habits and record how many hours/day they typically spend sitting while watching TV, using the computer, socializing, eating, reading, and driving or riding in a car (awareness of current behavior); information will then be provided on sedentary behavior and the health consequences of sitting too much (information dissemination); discussion of how participants could stand up and move more safely in their home environment (recommended behavior: stand up and move an extra 3-5 times/day); modeling (group leader stands and encourages others to stand up and move); discussion of **goal setting** and participants set a specific manageable goal on how to stand an added 3-5 times/day for the next week; development of an action plan to meet the goal (*Note:* participants will be asked to rate on their action plans their confidence in meeting the goal on a scale from 1, not confident at all to 10, completely confident. If a participant rates their confidence  $\leq 5$ , the facilitator will revisit the action plan to help older adults develop a different strategy in order to feel more confident); and discussion of **self-monitoring** (i.e., use of a click monitor and completion of a daily log at the end of each day to be brought back to the next session).

**Session 2:** group discussion on why they sit and barriers to standing up; examine behavior (from click monitors and daily logs) and goals from last week (**self-evaluation**); group discussion of strategies that worked, as well as barriers to standing more and then trouble shoot/problem solve (**feedback and information**); discussion of a list of strategies used in a study by Gardiner et al (2011); modeling (group leader stands and encourages others to stand and move); set **new goal** to increase standing and moving for next week (recommended behavior: stand up and move an extra 6-9 times/day); development of action plan to meet new goal (**corrective behavior**); and discussion of **self-monitoring**.

**Session 3:** discussion of behavior and goals from previous week (**self-evaluation**); confidence building (share successes and discuss incremental progress); discussion of cognitive reframing (i.e., how to reframe unhelpful thoughts); group discussion and information given on the benefits of standing and moving more; discussion of any problem areas with problem solving (**feedback**); modeling (group leader stands and encourages others to stand and move); set **new goal** to increase standing and moving for next week (recommended behavior: stand and move more an extra 10-12 times/day); develop action plan to meet new goal (**corrective behavior**); and discussion of **self-monitoring**.

**Session 4:** participants asked to reflect on their current sitting habits and record how many hours/day they spend sitting while watching TV, using the computer, socializing eating, reading, and driving or riding in a car (current behavior to compare to week 1); discussion of behavior and goals from last week (**self-evaluation**); information presented on relapse prevention and

recovery; discussion of how to stay active in the community; modeling; set new goals (i.e., **long term goal**); develop action plan to meet new goal (**continued behavior**); and discussion of **continued self-monitoring**.

*Note:* To support maintenance of behavior change, concepts that have been linked to maintenance of health behaviors will be integrated into the sessions, e.g., building relationships, autonomy, self-efficacy. In addition, a **refresher session** will be held at 8 weeks in which the facilitator will encourage participants to re-examine their motives for sitting less; discuss their progress and strategies that have been most effective, and barriers which have prevented them from standing up and moving more throughout the day. In addition, participants will revisit their goals with a focus on the future and long-term maintenance.

The intervention will be delivered via small group workshops. Research indicates the ideal range to facilitate active group discussions is 10-15 participants, thus, we will recruit 10-15 older adults per workshop in order to create an environment with enough people to have diversity in sharing and yet few enough to ensure that all participants can be involved in the discussions (*note:* this small group format worked well in our previous pilot research). Sessions will last between 1-1½ hrs and be held in locations in each county readily accessible to older adults (*note:* transportation will be provided to those older adults who require transport to the site). To enhance reach into the older adult communities in each county, the sessions will be facilitated by our community partners who regularly offer health promotion programs to older adults (see training of community partners and fidelity monitoring \*note below). The leaders will be trained to act more as facilitators than as lecturers. For example, rather than prescribing specific behavior changes, they will assist participants in making choices and achieving success in reaching self-selected goals. Instruction manuals with scripts will be provided to the leaders for each session to maximize fidelity of delivery of sessions per our intervention protocol.

